### 7.8.3 Safety Population

The Safety Population consists of all subjects who received a dose of study drug. Subjects will be analyzed based on treatment received.

### 7.8.4 Pharmacokinetic Full Population

The PK Full Population consists of all subjects who received a dose of RGLS8429 and have at least 1 concentration data point. Subjects will be analyzed based on dose received.

### 7.8.5 Pharmacokinetic Evaluable Population

The PK Evaluable Population consists of all subjects who received a dose of RGLS8429 and have at least one PK parameter that can be reliably estimated. Subjects will be analyzed based on dose received.

### 7.8.6 Biomarkers (Pharmacodynamic (PD)) Population

The Biomarker (PD) Population consists of all screened subjects who have at least one screening and/or pre-dose value for the biomarker parameters.

## 7.9 Subject Accountability

Summaries of analysis populations and subject disposition will be presented by cohort and overall. It will contain the following information:

- Number of subjects screened
- Number of subjects randomized
- Number and percent of subjects who completed the study
- Number and percent of subjects who discontinued early and reason for early discontinuation
- Number and percent of subjects in the Safety, PK Full, PK Evaluable, and PD Populations

Percentage will be calculated based on number of subjects in Randomized Population except for number of subjects screened.

Subject disposition data, exclusions from the analysis populations, eligibility criteria satisfaction and consent information will be presented in listings for the Randomized Population.

## 7.10 Protocol Deviations

All protocol deviations will be identified prior to database lock. Major protocol deviations will be listed. In addition, a separate listing of all inclusion and exclusion deviations will be provided.

## 7.11 Subject Demographics and Baseline Characteristics

Subject demographics (age, sex, race, and ethnicity) and baseline characteristics (height, weight, BMI, and eGFR) will be summarized descriptively based on the Randomized Population. Subject demographics and baseline characteristics will be listed.

## 7.12 Medical and Surgical History

The medical and surgical history data will be coded using the MedDRA, Version 24.0 or higher. and will be listed and summarized using the Randomized Population.

## 7.13 Prior and Concomitant Medications

All prior and concomitant medications will be coded using the WHO Global B3 format - March 2021. Concomitant Medications will be listed and summarized using the Safety Population. Prior Medications will be listed only for Randomized Population. A separate listing will be provided for concomitant procedures for Safety population.

## 7.14 Measurements of Treatment Compliance

A listing of treatment compliance will be provided for eCRF collected exposure data e.g expected dose, actual dose, number of injections etc. for the Randomized Population.

## 7.15 Pharmacokinetic Analysis

The PK Full Population will be used for all concentration (plasma and urine) listings, summary tables, and graphs. The PK Evaluable Population will be used for PK parameters listing (plasma and urine), PK parameters summary (plasma and urine), and statistical analysis.

The individual sampling and subject concentration-time for plasma drug concentrations of RGLS8429 will be listed and displayed graphically on linear and semi-log scales. The drug concentrations will be summarized descriptively by RGLS8429 cohort and nominal time point in tabular and graphical formats (linear and semi-log scales). Linear and semi-logarithmic plots of the individual plasma concentration by actual sampling time for each RGLS8429 cohort will be provided by subject (one subject per page). Overlay of individual plasma concentration profiles over time will be provided by RGLS8429 cohort. Plots of mean (SD) plasma concentration profiles versus time will be presented with all cohorts superimposed on the same plot.

All PK parameters will be listed. Summary statistics will be calculated for the plasma RGLS8429 PK parameters for each dose cohort using descriptive statistics to include, as appropriate, n, mean, SD, CV, Q1 and Q3, minimum, median, maximum, geometric mean and geometric %CV. For  $T_{max}$ , summary statistics will be described by n, minimum, median, and maximum only.

The total amount of RGLS8429 excreted in urine will also be assessed, where feasible. Urine pharmacokinetic parameters ( $CL_R$ , fe, Ae) will be listed for each subject by RGLS8429 cohort and summarized using descriptive statistics. Individual urine concentrations and volumes will be listed. In addition, urine samples will be qualitatively screened for potential RGLS8429 catabolites.

Additional PK parameters may be estimated as appropriate. The parameters stated above will be reported if they are estimable and will be discussed in the CSR. When necessary, interpolation or  $\lambda_z$  extrapolation may be used to estimate partial AUCs. The value of  $AUC\%_{extrap}$  will be less than or equal to 20% for the  $AUC_{inf}$  to be considered well estimated. If this proportion is > 20%, then the values of  $AUC_{inf}$  will be treated with caution. When  $AUC_{inf}$  is calculated and tabulated, the  $AUC\%_{extrap}$  will also be tabulated. Where  $AUC\%_{extrap} > 20\%$ ,  $AUC_{inf}$  and all related parameters (i.e. CL/F and Vz/F) will be presented but excluded from the calculation of summary statistics. All values excluded from the summaries should be flagged in the individual listings with an explanation for the exclusion.

The apparent terminal phase rate-constant ( $\lambda_z$ ) will be estimated by log-linear regression of the concentration-time data associated with this phase. The decision as to which data points describe the terminal phase will be reached by inspecting the semi-logarithmic plot of the data, only considering concentrations at time points beyond  $T_{max}$ . A minimum of three data points will be used for the estimation of  $\lambda_z$  preferably covering a time span of at least 2 half-lives. Poorly estimated  $\lambda_z$  (i.e. if a time span of at least 2 half-lives is not used or  $r^2_{adj} \leq 0.80$ ), the corresponding  $t_{1/2}$  and other parameters derived using  $\lambda_z$  (i.e.  $AUC_{inf}$ , CL/F, Vz/F, and  $t_{1/2}$ ) will be flagged in the report. Summary statistics of these parameters (i.e.  $AUC_{inf}$ , CL/F, Vz/F, and  $t_{1/2}$ )

will be reported with and without these outliers (i.e., with and without parameters where  $\lambda_z$  was poorly estimated).

### **Dose Proportionality Assessment:**

Dose proportionality will be explored using the power model for  $C_{max}$ ,  $AUC_{inf}$ ,  $AUC_{0-24}$  and  $AUC_{0-t}$  as data permit for the PK evaluable population.

A power model will be fit separately to describe the relationship between pharmacokinetic parameter ( $C_{max}$ ,  $AUC_{inf}$ ,  $AUC_{0-24}$  and  $AUC_{0-t}$ ) and actual dose in mg using the least-squares linear regression model as follows:

$$\ln(\text{PK parameter}) = \alpha + \beta \ln(\text{dose}) + \varepsilon.$$

This linear model will be used to provide a 95% confidence interval (CI) for  $\beta$  (slope).

From each pharmacokinetic parameter model, the intercept of the regression line  $\alpha$  and the slope of the regression line  $\beta$  will be presented along with the 95% CI of the slope. Actual dose of drug and not dose level will be used in analysis. A minimum of 3 non-missing PK parameter values per dose cohort must be available to estimate dose proportionality with the power model.

### **7.16 Biomarker Analysis**

The Biomarker (PD) Population will be used for all biomarker analyses. Baseline (the average of screening and Day -1 samples) biomarker data will be listed and summarized using descriptive statistics. Three summaries will be presented: Summary of Screening (Day -28 to Day-2), Summary of Day -1 and Summary of the average of Screening and Day-1 samples (Baseline).

### **7.17 Safety Analyses**

All Safety analysis will be presented using the Safety Population. No formal statistical tests will be conducted to assess the safety or tolerability of RGLS8429.

Tables will be presented by cohort and treatment group, pooled RGLS8429 and pooled placebo.

#### **7.17.1 Adverse Events**

All AE summaries will include TEAEs. TEAEs or TESAEs are those which occur or worsen after the administration of study drug until the Day 29 or EOS Visit whichever occurs later.

All AEs will be classified by primary system organ class (SOC) and preferred term (PT) according to the MedDRA Version 24.0 or higher. Data collected in CRF along with duration of AE will be presented in listing. Duration of AE will be calculated as stop date – start date.

The overall incidence of TEAEs (number and percentage of subjects) as well as the number of events will be summarized. It includes severity, relationship to study drug of TEAE and SAEs, TEAEs leading to study discontinuation, life-threatening SAEs, and SAEs resulting in death.

The TEAEs will be summarized and tabulated at both the subject (n [%] of subjects) and event (number of events) level:

- TEAEs by SOC and PT
- TEAEs by SOC, PT, and maximum reported severity
- TEAEs by SOC, PT, and relationship to study drug
- TESAEs by SOC and PT

For the incidence at the subject level by SOC and PT, if a subject experiences more than 1 event within the same SOC and PT, only 1 occurrence will be included in the incidence.

For the incidence at the subject level by SOC, PT, and severity, if a subject experiences more than 1 event within the same SOC and PT, only the most severe occurrence will be included in the incidence.

For the incidence at the subject level by SOC, PT, and relationship to study drug; if a subject experiences more than 1 event within the same SOC and PT, only the most closely related occurrence will be included in the incidence.

The incidence of DLTs will be summarized by cohort and treatment group.

Any SAEs, AEs with outcome of death and AEs resulting in discontinuation of study will be listed separately.

### **7.17.2 Clinical Laboratory Assessments**

Clinical laboratory data will be summarized using System International (SI) units and the Safety Population will be used.

Observed and change from baseline of continuous clinical laboratory values (serum chemistry, coagulation panel, hematology, lipids, and urinalysis) will be summarized for each parameter at each visit/timepoints using descriptive statistics.

Shift from baseline to worst post-baseline laboratory findings based on normal range criteria will also be summarized.

A listing of all clinical laboratory data for each subject at each visit will be presented. Laboratory values outside the reference range will be flagged with 'L' for low and 'H' for high in the data listings and a list of abnormal values will be presented.

For female subjects, serum/urine pregnancy test results during the study will be presented in the individual subject data listings.

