3.2. Dose Escalation and Stopping Rules

Prior to dose escalation, the Sponsor and the Investigator will perform a blinded review of the safety data (e.g., AE and safety laboratory tests through Day 15) on all subjects at the current dose level to make a dose escalation decision.

If 2 or more subjects at the same dose level experience the same or similar Grade ≥ 2 AEs (including clinically significant laboratory AEs) or if 1 subject experiences a Grade ≥ 3 AE or a SAE judged to be related to study drug, the Sponsor's Lead Physician will be unblinded to the treatment. Also, if 2 subjects develop stage 1 AKI or 1 subject develops stage 2 AKI the Sponsor's Lead Physician will be unblinded to the treatment.

The Sponsor's Lead Physician will determine whether the nature, severity, or number of event(s) warrants:

1. Continuing with the study as planned
2. Continuing with the study, but add additional safety evaluation(s)
3. Suspend dose escalation and enroll additional subjects at the same dose level
4. Add an intermediate-dose cohort or adjust the next dose level
5. Suspend or terminate the study

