4.2. Inclusion Criteria

Subjects must meet the following criteria to be eligible for study participation:

1. Male or female, 18 to 55 years of age
2. Continuous nonsmoker who has not used nicotine-containing products for at least 3 months prior to dosing
3. Body mass index (BMI) 18 to 35 kg/m²
4. Medically healthy, with no clinically significant medical history in the opinion of the Investigator.
5. Estimated glomerular filtration rate (eGFR) \geq 90 mL/min/1.73 m² (see [Section 2.3.3](#))
6. Platelet count within the normal limit
7. Hemoglobin concentration within the normal limits
8. Liver function tests (ALT, AST, ALP, and bilirubin [total and direct]) must be \leq the ULN
9. Female subjects of childbearing potential must not be lactating and must have no plans to become pregnant during the course of the study through 28 days after the administration of study drug. Female subjects of childbearing potential who are heterosexual must agree to use one of the following methods of contraception considered to be highly effective (i.e., results in <1% failure rate when used consistently and correctly) from Screening through 28 days after the administration of study drug
 - a. Intrauterine device (IUD) or intrauterine system (IUS) in place for at least 3 months prior to study drug administration
 - b. Partner has had a vasectomy. Vasectomy in the partner is considered to be highly effective only if the partner is the sole sexual partner of the female subject of childbearing potential and had his vasectomy performed 6 months or more prior to randomization.
 - c. Stable hormonal contraception associated with inhibition of ovulation (with approved oral, transdermal, or depot [e.g., NuvaRing, depot injection, etc.] regimen) for at least 3 months prior to study drug administration
10. A female subject of non-childbearing potential must have undergone one of the following sterilization procedures at least 6 months prior to administration of study drug:
 - a. Hysterectomy
 - b. Bilateral oophorectomy
 - c. Bilateral tubal occlusion

d. Bilateral salpingectomy

or be postmenopausal with no menstrual periods for at least 1 year prior to administration of study drug.

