8.4.3. Safety Analysis

The Safety Population will be used for all safety analyses. No formal statistical tests will be conducted to assess the safety or tolerability of RGLS8429.

Subject incidence of all TEAEs, all TEAEs related to study drug, and all SAEs will be tabulated by system organ class and preferred term. All fatal adverse events, SAEs, and TEAEs leading to withdrawal from study drug will also be listed.

The incidence of DLTs will be summarized by dose level and treatment group.

The analyses of safety laboratory tests, vital signs, and ECGs will include summary statistics over time tabulated by cohort. Similarly, changes from baseline will be summarized. Shifts based on normal ranges between the baseline and the worst on-study value will be tabulated by dose level and treatment group.

The results from the central reader assessment of ECGs extracted from the Holter data will be used in all statistical analysis. The following intervals will be summarized by treatment group: PR, QRS, RR, HR, uncorrected QT, QTcB, and QTcF. Details of additional analyses will be provided in the Statistical Analysis Plan.

The total dose of study drug and the proportion of subjects receiving each dose level will be summarized using descriptive statistics.

Changes from baseline in the SARA test scores will be summarized descriptively over time and by treatment cohort for each category and the total score. The SARA is a tool for assessing ataxia. It has eight categories with accumulative score ranging from 0 (no ataxia) to 40 (most severe ataxia). When completing the outcome measure, each category is assessed and scored accordingly. Scores for the eight items range as follows:

1. Gait (0-8 points),
2. Stance (0-6 points),
3. Sitting (0-4 points),
4. Speech disturbance (0-6 points),
5. Finger chase (0-4 points),
6. Nose-finger test (0-4 points),
7. Fast alternating hand movement (0-4 points),

8. Heel-shin slide (0-4 points).

Once each of the 8 categories has been assessed, the total is calculated to determine the severity of ataxia.

For motor activities of the four extremities (Items 5-8), assessments are performed bilaterally, and the mean values are used to obtain the total score.

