9.2.2. Severity/Intensity

For both AEs and SAEs, the Investigator must assess the severity/intensity of the event.

The Investigator will assess the grade of the AE according to the FDA's Guidance for Industry: Toxicity Grading Scale for Healthy Adult and Adolescent Volunteers Enrolled in Preventive Vaccine Clinical Trials (September 2007) except for AEs associated with abnormal serum creatinine level. The Investigator will use the KDIGO Clinical Practice Guideline for Acute Kidney Injury (<https://kdigo.org/wp-content/uploads/2016/10/KDIGO-2012-AKI-Guideline-English.pdf>) to grade the severity of an AE associated with abnormal serum creatinine level. Toxicities that are not specified in these guidances will be defined as follows:

- Grade 1: Mild; asymptomatic or mild symptoms; clinical or diagnostic observations only; intervention not indicated
- Grade 2: Moderate; minimal, local, or noninvasive intervention indicated; limiting age-appropriate instrumental activities of daily living (ADL)
- Grade 3: Severe or medically significant but not immediately life-threatening; hospitalization or prolongation of hospitalization indicated; disabling; limiting self-care ADL
- Grade 4: Life-threatening consequences; urgent intervention indicated
- Grade 5: Death related to AE

The term “severe” is often used to describe the intensity of a specific event (as in mild, moderate, or severe myocardial infarction); however, the event itself may be of relatively minor medical significance (such as severe headache). This criterion is *not* the same as “serious”, which is based on subject/event *outcome* or *action* criteria associated with events that pose a threat to a subject’s life or functioning.

Seriousness, not severity, serves as a guide for defining regulatory obligations.

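### Laboratory shift tables by normal range alone do not show, by dose, how many subjects reached the toxicity grades or AKI stages that the protocol's unblinding rule uses

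*SAP*

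**What the plan says.** **What is tabulated.** SAP 7.17.2: "Shift from baseline to worst post-baseline laboratory findings based on normal range criteria will also be summarized". This becomes Table 14.3.5.2 in SAP Section 9. Protocol 8.4.3 has the same rule: "Shifts based on normal ranges between the baseline and the worst on-study value will be tabulated by dose level and treatment group". Listings carry direction only: "Laboratory values outside the reference range will be flagged with 'L' for low and 'H' for high in the data listings". SAP Section 9 lists no laboratory table by toxicity grade, multiple of the ULN or KDIGO stage.

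**What the protocol acts on.** Under Protocol 3.2, the Sponsor's Lead Physician is unblinded if two or more subjects at a dose level have the same or a similar AE of Grade 2 or above (clinically significant laboratory AEs count), or if one subject has a related Grade 3 or higher AE or a related SAE. The renal criterion is met "if 2 subjects develop stage 1 AKI or 1 subject develops stage 2 AKI".

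**Which scales apply.** Protocol 9.2.2: "The Investigator will assess the grade of the AE according to the FDA's Guidance for Industry", with an exception for creatinine: "The Investigator will use the KDIGO Clinical Practice Guideline for Acute Kidney Injury", used "to grade the severity of an AE associated with abnormal serum creatinine level".

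**Where subjects start.** Protocol 4.2, criterion 8: "Liver function tests (ALT, AST, ALP, and bilirubin [total and direct]) must be" no higher than the ULN.

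**The concern.** Change in safety laboratory results is part of the primary endpoint (Protocol 2.2, SAP 2.2.1). The protocol judges such changes by size, using a grade for most analytes and a stage relative to the subject's own value for creatinine. The shift table records only whether a value is low, normal or high.

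Two kinds of information drop out of the summary: the size of a liver elevation, and a creatinine rise that ends inside the reference range. Both organs matter here. Protocol 1.3 reports dose-limiting hepatotoxicity in the 13-week mouse study, the species on which Protocol 1.4 bases the starting dose, and AKI is named in the escalation rule. A reader of the final report could not take from any planned table the number of subjects per dose who reached a given ALT grade or AKI stage.

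**Working it through.** The documents give no figure to reproduce on this point, and the safety analysis is descriptive. The check is how particular records would be classified.

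**Liver (no outside figure needed).** Baseline is the last value before dosing (SAP 7.1), and entry requires ALT and AST at or below the ULN. For a subject whose baseline is within range, any post-dose value above the ULN goes to normal-to-high. As an illustration, peaks of 1.2 × ULN and 6 × ULN fall in the same cell.

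**Creatinine (general rule).** Let *b* be a baseline within the normal range.
- A rise to *r* × *b* stays normal-to-normal when *r* × *b* ≤ ULN, so when *b* ≤ ULN/*r*. For *r* = 1.5, 1/1.5 = 0.67 of the ULN. For *r* = 2, 1/2 = 0.50 of the ULN.
- A rise of *d* stays normal-to-normal when *b* ≤ ULN − *d*.

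**Creatinine (assumed figures).** Assumptions: ULN 1.17 to 1.35 mg/dL for men and 0.95 to 1.20 mg/dL for women; stage 1 at 1.5 × baseline or +0.3 mg/dL; stage 2 at 2 × baseline.

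| Rise | Men: stays in range if baseline is at most | Women: stays in range if baseline is at most |
|---|---|---|
| +0.3 mg/dL | 1.17 − 0.3 = 0.87 to 1.35 − 0.3 = 1.05 | 0.95 − 0.3 = 0.65 to 1.20 − 0.3 = 0.90 |
| × 1.5 | 1.17/1.5 = 0.78 to 1.35/1.5 = 0.90 | 0.95/1.5 = 0.63 to 1.20/1.5 = 0.80 |
| × 2 | 1.17/2 = 0.585 to 1.35/2 = 0.675 | 0.95/2 = 0.475 to 1.20/2 = 0.60 |

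Examples:
- A woman going from 0.60 to 0.90 mg/dL has a ratio of 1.5 and a difference of 0.30. She would be stage 1 on either assumption, and 0.90 lies below every assumed female ULN, so she is tabulated normal-to-normal.
- A man going from 0.80 to 1.10 mg/dL has a difference of 0.30 and a ratio of 1.375. He would be stage 1 on the +0.3 assumption only, and 1.10 lies below every assumed male ULN.

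**Do other planned outputs supply the count?**
- *TEAEs by maximum severity (SAP 7.17.1).* These show a laboratory change only if it was reported as an AE. Protocol 9.3 requires study discontinuation, an intervention, or a judgement of clinical significance. Protocol 9.2.2 applies KDIGO to AEs with abnormal creatinine, so an in-range rise might never be staged.
- *Listing of abnormal results (Table 14.3.4).* This omits in-range values by construction.
- *By-visit observed and change summaries.* They show the size of change, including the minimum and maximum, but do not count subjects by grade or stage. SAP 7.1 leaves unscheduled and repeat values out of descriptive statistics, and a peak may fall there.
- *DLT table (14.3.1.6).* The text available to me defines no DLT, so the table cannot be assumed to carry ALT grade or AKI stage.
- *Full laboratory listing (16.2.8.2).* It holds every value, but the reader would have to derive grades and stages by hand.

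**The case against.** The case for leaving the plan as it is has weight.

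- **Magnitude is not hidden.** With 32 subjects and five scheduled post-dose chemistry draws (Days 2, 8, 15, 22 and 29), there are 32 × 5 = 160 scheduled creatinine values, all listed by subject and visit. This stands: mild and severe ALT rises look alike in one table, not throughout the report.
- **Recognised events would be reported.** An AKI noticed for the Protocol 3.2 rule, or an ALT many times the ULN, would ordinarily become an AE, be graded and be tabulated by maximum severity. This largely stands. The remaining gap is mainly the smaller rise that nobody judged clinically significant, and the lack of a count that does not depend on that judgement.
- **Not every subject is affected.** The creatinine problem concerns lower baselines. The Protocol 2.3.3 formula allows an 18-year-old man to enter at about 1.20 mg/dL. A 1.5-fold rise gives 1.80, which is above every assumed ULN and would be flagged high.
- **The scales were adopted for grading AEs.** Protocol 9.2.2 does not ask for programmed grading of every laboratory value. This is correct, so the proposal adds a derivation.

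A reader might also infer more than the documents support:
- *That one stage 1 AKI triggers unblinding.* It does not. The rule needs two subjects at stage 1, or one at stage 2.
- *That escalation decisions would be impaired.* They rest on review of accumulating data under Protocol 3.2, and the SAP outputs follow database lock (SAP Section 5).
- *That the SAP departs from the protocol.* Protocol 8.4.3 has the same normal-range rule.
- *That an eGFR still above 90 after a rise proves the point.* eGFR is an entry criterion calculated at Screening and does not classify anything in the shift table.

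**Conclusion.** The point holds as a gap in summary display. No planned table counts, by dose, the subjects whose laboratory values reached the grades or AKI stages that the unblinding rule uses.

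The liver part follows from the documents alone: from a normal baseline, every elevation shares one cell whatever its size. The creatinine part holds for any stage defined against the subject's own baseline. On the assumption of 1.5 times baseline for stage 1, it applies to baselines at or below about 0.67 of the ULN. The mg/dL cut-offs depend on assumed ULNs and thresholds and should be recalculated with the laboratory's actual limits.

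Direction of change is probably kept (the L and H flags suggest low, normal and high categories), the data are complete in the listings, and study conduct is unaffected. This is a worthwhile improvement to the reporting of a primary-endpoint component, not the correction of an error.

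**What to change.** In SAP 7.17.2 and the Section 9 table list, add:

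1. A shift from baseline to the maximum post-dose grade on the FDA scale cited in Protocol 9.2.2, for each analyte that scale grades.
2. The number and percentage of subjects by maximum post-dose KDIGO creatinine stage, with creatinine taken against the subject's own baseline.

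Present both by dose level and for pooled placebo. Compute them from the laboratory values, not from AE reports. State that unscheduled and repeat values count towards the maximum, as an exception to the general rule in SAP 7.1. Print the thresholds used in the SAP. Keep the normal-range shift for tests without a grade.

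The cost is one or two extra tables and a programmed derivation from data already collected, on scales the protocol already cites. Sample size, visits and study conduct do not change.
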